2.6 Sample Size Determination

This study plans to randomize 200 participants, which will provide 94% power (alpha = 0.05) to detect a difference between a 27% reduction in pain intensity in the propranolol arm and a 9% reduction in the placebo arm (primary hypothesis). Assuming haplotype distributions and within-haplotype treatment effects that are similar to those observed in the pilot study, the same sample size would provide 61% power (alpha = 0.05) to detect an interaction between haplotype and treatment group (secondary hypothesis).

Power calculations were made using the GLMPOWER procedure in SAS, which assumes a data structure of one observation per person. This is a simplification of the situation that will occur with the linear mixed model, described in Section 10.4.1, where efficacy will be evaluated using a data structure where most participants will have three observations per person. The simplified power calculations are shown here because conventional software for power calculations does not deal with the more complex situation of linear mixed models.

3. GENERAL ANALYSIS AND REPORTING CONVENTIONS

The following is a list of general analysis and reporting conventions to be applied for this study.

- Categorical variables will be summarized using counts (n) and percentages (%) and will be presented in the form n (%).
- Moment statistics including mean and standard deviation will be reported at 1 more significant digit than the precision of the data.
- Order statistics including median, min, and max will be reported to the same level of precision as the original observations. If any values are calculated to have more significant digits then the value should be rounded so that it is the same level of precision as the original data.
- Following SAS default rules, the median will be reported as the average of the two middle numbers if the dataset contains even numbers.
- Test statistics including t and z test statistics will be reported to two decimal places.
- P-values will be reported to 3 decimal places if greater than 0.001. If less than 0.001, then p-values will be reported as <0.001. P-values will be reported with a leading 0, e.g., 0.05 rather than .05.
- No preliminary rounding should be performed; rounding should only occur after analysis. To round, consider digit to right of last significant digit: if < 5 then round down, if >=5 then round up.

Version 3.0 Page 7 of 25

• All listings will be sorted in order of treatment group (e.g., active, placebo), participant, and time of assessment (e.g., visit, time, and/or event).

If departures from these general conventions are present in specific sections of this SAP, then those conventions will take precedence over these general conventions.

The items listed below will apply to all data analyses.

- For categorical variables, summary statistics will consist of the number and percentage of patients in each category. All percentages will be rounded to one decimal point. The number and percentage of patients will always be presented in the form XX (XX.X) where the percentage is in parentheses. To ensure completeness, all summaries for categorical and discrete variables will include all categories, even if none of the patients had a response in a particular category. Unless otherwise noted, for all percentages, the number of patients in the analysis population for the treatment group who have an observation will be the denominator.
- For continuous variables, summary statistics will consist of the number of patients, mean, median, standard error of the mean (SE), minimum, and maximum values. The summary statistic n will be the number of patients with non-missing values. All means and medians will be reported to one more significant digit than the values being analyzed. Standard errors will be reported to two more significant digits than the values being analyzed. The minimum and maximum will be reported to the same number of significant digits as the values being analyzed.
- For tests of hypothesis of treatment group differences, the associated P-value will be reported.
- Version 9.4 or later of the SAS® software package will be used to produce all summaries, listings, statistical analyses, and graphical presentations.

4. ANALYSIS POPULATIONS

4.1 Intention-to-Treat Population

Section 11.3.1 of the protocol defines the intention-to-treat (ITT) sample as follows:

Consistent with the primary statistical method that will use a linear mixed model, the intention-to-treat (ITT) sample is defined as all study participants who have at least one valid measurement of the primary endpoint (at Visit 2 or later. A "valid" assessment for the primary endpoint is defined as at least 4 daily reports of pain intensity and duration collected in the 7-day period prior to the visit (Section 2.5.1 of the protocol). Treatment group allocation will be defined as the study arm into which the subject was randomized regardless of the actual study treatment received. By necessity, the ITT sample excludes participants who provide no data for the primary endpoint after randomization. Note that follow-up

Version 3.0 Page 8 of 25

assessments will be included in the ITT analysis when sufficient diary data are collected at the follow-up assessment, even if there were protocol violations. Likewise, the ITT sample will include all available follow-up assessments from any discontinued participants.

4.2 Per-Protocol Population

As stated in Section 11.3.2 of the protocol, the per-protocol (PP) sample will be a subset of the ITT sample, excluding any assessments made at or after a visit at which the participant is found to have any major protocol deviation as listed in Section 5.2 below and excluding all assessments for participants whose compliance with study medication is less than 60% over all the study visits.

4.3 Safety Population

Section 11.3.3 of the protocol defines the safety population as follows:

The safety sample will include all randomized participants who received at least one dose of study medication. Participants in the safety sample will be analyzed with the treatment group according to the medication they actually received, regardless of their randomized assignment.

All adverse events (AEs) will be recorded on a case report form regardless of study population. For safety analyses, all AEs will be provided in listings, but only treatment emergent adverse events (TEAEs) within the safety population will be reported in summary tables.

5. STUDY PATIENTS

5.1 Disposition of Patients

The screened population will consist of all consented participants and the randomized population will consist of all screened participants who are randomized. Any participant who does not meet the criteria for randomization with be discontinued from the trial. Participants who withdraw from the study voluntarily or are withdrawn by an investigator will be discontinued from the study. Study staff will complete a study disposition form in the electronic data capture system, indicating the reason for discontinuation. The disposition of all participants and the study populations to which they belong will be presented in the participant listings and summarized by treatment allocation in a disposition table.

5.2 Protocol Deviations

The protocol deviations listed below are related to the use of investigational product and concomitant therapies and will be considered major protocol deviations. These deviations will exclude a participant's data from the PP analysis (Section 4.2).

Version 3.0 Page 9 of 25

- Participant is unable to reach the maintenance dosage of the study drug or placebo or is unable to remain on the maintenance dosage.
- Initiation of opioid medications.
- Initiation of TMJ surgical treatment (including TMJ arthrocentesis).
- Initiation of therapeutic injections for the management of pain.
- Initiation of occlusal appliance therapy.
- Initiation of any of the following non-pharmacological therapies: acupuncture, biofeedback, and/or TENS.
- Initiation after Visit 1 and usage between Visits 1 and 4 of short-acting, non-prescription analgesics (e.g., NSAIDs, aspirin, and/or acetaminophen) for pain that exceeds the definition of episodic use as described in Section 5.7.1 of the protocol.

These and other types of protocol deviations will be reported during the study. The types of protocol deviations will be summarized descriptively for both the Safety and ITT populations by treatment group. A listing of the protocol deviations of individual participants will be included in the participant listings.

6. DEMOGRAPHIC AND OTHER BASELINE CHARACTERISTICS

Demographic and other baseline characteristics will be summarized descriptively for both the ITT and the PP populations. While no formal statistical testing will be done, all demographic and baseline characteristics will be assessed for clinically significant differences between the treatment groups. P-values from these comparisons will be considered descriptive.

To further assess the overall health of the study participants prior to study treatment, any significant medical history will be included in the participant listings.

All prior and concomitant medications will be coded to preferred drug names and therapeutic drug class using the *WHO Drug Dictionary*. Use of concomitant medications will be summarized for each therapeutic drug class and each preferred drug name. Concomitant medications will include medications reported on the Concomitant Medications page of the CRF.

7. MEASUREMENTS OF TREATMENT COMPLIANCE

Participants will be asked to bring their medication containers to each visit during the treatment period. Study staff will count the number of capsules returned and will enter the number on a case report form in the electronic data capture system. Participants will also record the study medication use in their Daily Symptom Diary that will be reviewed by the study staff at Visits 2, 3, 4, and 5. Participant compliance with study medication will be defined as taking 60% or more of the study medication over all study visits. In reports, pill counts will supersede the Daily Symptom Diary in determining compliance. Treatment compliance will be summarized by treatment group and ITT population.

Version 3.0 Page 10 of 25

8. EFFICACY EVALUATION

8.1 Handling of Dropouts or Missing Data

There will be no imputation for missing data. Missing data will be accommodated in the linear mixed model.

8.2 Efficacy Variables

The efficacy variables are listed and described in Table 8-1.

Table 8-1 Efficacy Variables

Efficacy Variables	Description and Derivation
Primary	
Net Change in the Mean Pain Index	The weekly mean pain index will be computed for the week prior to randomization and for each week during the treatment phase. The weekly mean pain index will be based on at least 4 daily reports of facial pain intensity and duration collected in the 7-day period prior to the visit. When there are fewer than 4 daily reports, the weekly mean pain index will be considered missing. The net change in the mean pain index will be calculated as the weekly mean pain index at V2, V3, or V4 minus the weekly mean pain index at V1.
30% Responder Status	The binomial 30% responder status will be positive if the participant experiences a decrease of 30% from V1 in their TMD weekly mean pain index at V4.
50% Responder Status	The binomial 50% responder status will be positive if the participant experiences a decrease of 50% from V1 in their TMD weekly mean pain index at V4.
Secondary	
Net Change in the Mean Pain Intensity	The weekly mean pain intensity will be based on at least 4 daily reports of facial pain intensity collected in the 7-day period prior to the visit. When there are fewer than 4 daily reports, the weekly mean pain intensity will be considered missing. The net change in the mean pain intensity will be calculated as the weekly mean pain intensity at V2, V3, or V4 minus the weekly mean pain intensity at V1.
Net Change in the Mean Pain	The weekly mean pain duration will be based on at least 4

Version 3.0 Page 11 of 25

Efficacy Variables	Description and Derivation
Duration	daily reports of facial pain duration collected in the 7-day period prior to the visit. When there are fewer than 4 daily reports, the weekly mean pain duration will be considered missing. The net change in the mean pain duration will be calculated as the weekly mean pain duration at V2, V3, or V4 minus the weekly mean pain duration at V1.
Quantitative sensory tests of sensitivity to experimental pain (QST form)	For each visit when it was measured, Thermal Pain Tolerance, recorded in degrees Celsius, will be computed as the mean of 4 pain tolerance trials. For each visit when it was measured, Thermal Pain Threshold recorded in degrees Celsius, will be computed as the mean of 4 pain threshold trials.
Pressure Pain Threshold (DC/TMD exam)	For each visit when they were measured, five variables, recorded in kg, representing mean Pressure Pain Threshold at each of five anatomical locations: a) Temporalis muscle, b) Masseter muscle; c) TMJ; d) Trapezius muscle; and e) lateral epicondyle eminence (item 8 of DC/TMD Exam form). At each site, the mean response to two trials, each performed bilaterally, will be computed. For each trial, threshold is defined as the amount of pressure at which the participant first perceives the stimulus to be painful
Facial pain ratings (SF-McGill questionnaire)	For each visit when it was administered, two subscales, each a continuous variable, will be computed from the Short Form McGill Pain Questionnaire: a) Affective component, and b) Sensory component. In addition, 4 variables assessing facial pain will be analyzed: a) Present Pain Intensity (Item II of the SF-McGill); b) Weekly Pain Intensity (Item III of the SF-McGill); c) Weekly Pain Duration (Item IV of the SF-McGill); and d) Weekly Fatigue (Item V of the SF-McGill).
Clinical measures of limitation in jaw function (DC/TMD Exam)	For each visit when they were measured, the following clinical measures will be derived. Three measurements of range of jaw motion will be analyzed, each recorded in millimeters: a) Pain-free jaw opening; b) Maximum unassisted jaw opening; and c) Maximum assisted jaw opening (Item 4 of the DC/TMD form) The count of clinical pain masticatory structure locations

Version 3.0 Page 12 of 25

Efficacy Variables	Description and Derivation
	where pain is reported during the 30-day period prior to examination: temporalis muscles, masseter muscles, other masticatory muscles, and TMJs, each reported bilaterally (Item 1a of DC/TMD form).
	The count of examination hyperalgesia masticatory structure locations will be computed (range=0 to 8) representing places in which pain is elicited during jaw provocation during the examination: temporalis muscles, masseter muscles, other masticatory muscles, and TMJs, each reported bilaterally (Items 4, 5 and 6 of DC/TMD form). Jaw provocation includes jaw mobility maneuvers and standardized pressure palpation.
	The count of examination familiar pain masticatory structure locations will be computed (range=0 to 8) representing places in which pain is elicited during jaw provocation during the examination: temporalis muscles, masseter muscles, other masticatory muscles, and TMJs, each reported bilaterally, and confirmed by the subject to be familiar to pain experienced in the prior 30 days (Items 4, 5 and 6 of DC/TMD form). Jaw provocation includes jaw mobility maneuvers and standardized pressure palpation.
Vital signs	For each visit when it was measured, systolic and diastolic blood pressure (recorded in mmHg) and heart rate (recorded in beats per minute) will be computed, each as the mean of three repeated measurements taken 2 min apart and recorded as Vital Signs in RAVE.
Subjective health status (SF-12v2 questionnaire)	For each visit when it was administered, published scoring algorithms will be used to compute two continuous variables from the SF-12v2 questionnaire: a) Physical Component Subscale and b) Mental Component Subscale (SF-12v2 questionnaire).
Headache Impact (HIT-6 questionnaire)	For each visit when it was administered, published scoring algorithms will be used to compute the Total Score for headache impact, a continuous variable.
Graded chronic pain ratings (GCPS questionnaire)	For each visit when it was administered, published scoring algorithms will be used to compute two continuous measurements (Characteristic Pain Intensity and Pain Interference) and one derived ordinal score (Grade of Chronic Pain) from the GCPS questionnaire.

Version 3.0 Page 13 of 25

Efficacy Variables	Description and Derivation
Anxiety and Depression (HADS questionnaire)	For each visit when it was administered, published scoring algorithms will be used to compute two continuous measurements: Anxiety, and Depression scores.
Patient global impression of change (PGIC questionnaire)	The ordinal rating of change, measured at the subject's visits 3 and 4, will be reported as two secondary outcome variables.
Subjective measure of jaw functional limitation (JFLS questionnaire)	For each visit when it was administered, published scoring algorithms will be used to compute four continuous scores of subjective jaw function from the JFLS questionnaire: a) Chewing Limitation b) Opening Limitation; c) Verbal & Emotional Expression Limitation; and d) Combined Global Measure.
Psychological Stress (PSS questionnaire)	For each visit when it was administered, published scoring algorithms will be used to compute a continuous summary score of psychological stress from the PSS questionnaire.
Somatic symptoms (SCL-90R questionnaire)	For each visit when it was administered, published scoring algorithms will be used to compute the Somatization Scale from the SCL-90R questionnaire.
Sleep quality (PSQI questionnaire)	For each visit when it was administered, published scoring algorithms will be used to compute the global measure of sleep quality from the PSQI questionnaire.

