## 8 ASSESSMENT OF SAFETY

### 8.1 Specification of Safety Parameters

Participants in this study will undergo close follow-up. As described in Section 2.3, risks related to participation include: 1) risks related to the administration of propranolol hydrochloride extended-release; 2) risks related to the administration of the ECG; 3) risks associated with questionnaires; 4) risks associated with TMD examinations and psychophysical tests; 5) well-known and anticipated minor risks from venous phlebotomy; and 6) risks related to study participation such as loss of confidentiality of collected data.

The risks described above will be characterized and monitored to protect the safety of participants. In addition, the study has been designed to minimize risks. Participants will be monitored closely for AEs with frequent visits. Adverse events will be managed by the site dentist or site cardiologist depending on the nature of the event.

---

Examination and close follow-up of parameters capturing participants' overall health will be collected on case report forms. These will be completed at every study visit, and data will be compiled into a prespecified format and reviewed by the DSMB (Section 9).

As part of the study outcomes, study personnel will collect the occurrences of the following expected AEs known to be associated with propranolol hydrochloride extended-release:

- Dizziness or lightheadedness
- Unusual tiredness or fatigue
- Nausea or vomiting
- Upset stomach
- Hands numbness or tingling
- Sleep problems
- Depression

In this study, the following expected events will not be considered reportable AEs:

- Minor bleeding or bruising resulting from the blood draw
- Temporary pain or temporary increases in existing pain elicited during the TMD clinical examination or tests of heat, pressure, or tender points
- Worsening of TMD signs and symptoms during the participant's 12- to 15-week participation

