There are approximately 20 participants that were enrolled early at UB who did not have the "type of pain" documented when taking over-the-counter analgesics. It cannot be known whether the over-the-counter analgesics were taken due to TMD pain (i.e., rescue medications) and thus these 20 participants will be excluded from the above treatment group effects on the rescue medication use analysis. These subjects will be included in the use of over-the-counter analgesics for any pain.

All of the above secondary efficacy analyses are secondary to and supportive of the primary hypothesis analysis, and thus no statistical corrections will be made for multiplicity for any of the secondary analyses. P-values ≤ 0.05 will be considered statistically significant.

Additional secondary analyses of the incidence of adverse events are described in Section 9.

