9.4 Vital Signs and Other Observations Related to Safety

Listings will include all participant vital signs and any other comments as provided by the examining clinician. Vital signs statistics will be summarized in table form by treatment group and study visit. These tables will include summary statistics appropriate for variable type as listed in Section 3.

Version 3.0 Page 19 of 25

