11. CHANGES TO THE ANALYSES PLANNED IN THE PROTOCOL

No changes to the analyses planned in the protocol have been made.

Version 3.0 Page 21 of 25

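### SAP Table 8-1 files blood pressure and heart rate as secondary efficacy variables, so a pharmacodynamic effect of propranolol could be reported as a significant efficacy result without any analgesia

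*SAP*

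**What the plan says.** SAP 8.2 introduces its table with "The efficacy variables are listed and described in Table 8-1". In the secondary block, the vital signs row reads "For each visit when it was measured, systolic and diastolic blood pressure (recorded in mmHg) and heart rate", each taken as the mean of three readings. SAP 8.3.2 applies the primary mixed model to every secondary measure that is continuous or a count, and reports treatment P-values overall and at each visit. SAP 8.3 makes ITT the default population. SAP 8.3.2 then states: "All of the above secondary efficacy analyses are secondary to and supportive of the primary hypothesis analysis". On that ground it makes no multiplicity correction, and it calls P ≤ 0.05 statistically significant.

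The same measurements appear again as safety assessments in SAP 9.1. There the plan is descriptive: "Vital signs statistics will be summarized in table form by treatment group and study visit" (SAP 9.4).

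In the facial pain row of Table 8-1, after the two SF-McGill subscales, the SAP says "In addition, 4 variables assessing facial pain will be analyzed". The fourth of these is weekly fatigue, Item V of the SF-McGill form. Protocol 8.1 lists "Unusual tiredness or fatigue" among the adverse events known to be associated with extended-release propranolol.

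SAP 11 declares: "No changes to the analyses planned in the protocol have been made".

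**The concern.** Secondary efficacy results are read as evidence on whether the drug helps the condition. In a TMD pain trial, lower heart rate or blood pressure is not such evidence. It is what the package insert in Protocol Appendix B describes as the drug's pharmacology, and the insert lists bradycardia and hypotension as adverse reactions. The SAP sets no direction of benefit for these variables and does not exempt them from the general rule in 8.3.2. Followed literally, the plan can add significant P-values to the supportive evidence even if pain is unchanged.

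The filing also has a cost on the safety side. The only formal between-arm comparison of vital signs is the efficacy one, in a population defined by diary completion. A participant who took study drug and left without a valid diary week at Visit 2 or later is outside that comparison, yet may be someone whose heart rate or pressure readings matter.

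The fatigue label is a smaller matter. It places a symptom that the drug is expected to worsen in a row of pain ratings.

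**Working it through.** **1. Is the classification in the protocol?**

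| Place | Content | BP or heart rate named? |
|---|---|---|
| Protocol 2.4.2 | pain ratings; experimental pain; physical and emotional function and global change; symptoms and AEs; rescue medication | no |
| Protocol 2.5.2 | diary intensity and duration; clinical, heat and pressure pain; jaw function; health and emotional status; global improvement; sleep; somatic symptoms; AEs; rescue medication | no |
| Protocol 11.1.2 | pain, pain sensitivity, function and global improvement, rescue and over-the-counter analgesics | no |
| Protocol 2.3.1 | resting blood pressure and heart rate monitored, under the risks of the drug | yes, as risk monitoring |
| SAP Table 8-1 | secondary efficacy | yes, three variables |
| SAP 9.1, 9.4 | safety, descriptive | yes |

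Protocol 2.5.2 refers to Section 7.1 for methods, and 7.1.2 describes vital signs, but the list of outcomes in 2.5.2 does not include them.

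**2. What would the planned test do?** The plan gives no figure for this point to reproduce, and the documents give no effect or SD for heart rate or blood pressure. The following inputs are therefore assumptions: n = 90 per arm (100 randomised per arm, less the 10% loss in Protocol 11.2), two-sided 0.05, SD of heart-rate change 10 to 12 bpm, true difference 5 or 8 bpm.

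Power ≈ Φ(δ / SE − 1.96), with SE = SD × √(2/n) and √(2/90) = 0.1491.

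| δ (bpm) | SD | SE | δ/SE | δ/SE − 1.96 | Power (normal) | Power (t-test) |
|---|---|---|---|---|---|---|
| 5 | 10 | 1.491 | 3.354 | 1.394 | 91.8% | 91.6% |
| 5 | 12 | 1.789 | 2.795 | 0.835 | 79.8% | 79.4% |
| 8 | 10 | 1.491 | 5.367 | 3.407 | >99.9% | >99.9% |
| 8 | 12 | 1.789 | 4.472 | 2.512 | 99.4% | 99.4% |

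In standardised units, with 90 to 100 per arm, power is 52% to 56% at 0.3, 77% to 81% at 0.4 and 92% to 94% at 0.5. The same figures would apply to systolic or diastolic pressure at those standardised differences; no separate effect for pressure is assumed here.

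**3. Does it matter through multiplicity?** Table 8-1 yields 41 secondary variables: diary intensity and duration 2, thermal 2, pressure threshold 5, SF-McGill 6, jaw examination 6, vital signs 3, SF-12 2, HIT-6 1, GCPS 3, HADS 2, PGIC 2 (two visits), JFLS 4, PSS 1, SCL-90R 1, PSQI 1. If every null were true and the tests were independent (illustrative only, since the outcomes are correlated), the chance of at least one P ≤ 0.05 is 1 − 0.95^k:

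- k = 41: 87.8%
- k = 38 (vital signs removed): 85.8%
- k = 37 (fatigue also removed): 85.0%

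The count hardly matters. The problem is that these tests can be truly positive through pharmacology that is not analgesia.

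**4. Which participants are compared?** SAP 4.1 (ITT) requires at least one valid diary week at Visit 2 or later and groups by randomised arm. SAP 4.3 (Safety) requires one dose and groups by medication received. The P-values for vital signs come from the first set; the second gets summary statistics only.

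**The case against.** The strongest reply is that little practical harm follows. The row is plainly headed as vital signs, SAP 9.1 separately calls the same data safety data, and the sentence about supportive analyses is there to justify the absence of a multiplicity correction, not to declare each P-value evidence of pain relief. Protocol 11.4.2 defers detail on the secondary efficacy variables to the SAP, and Protocol 2.4.2 itself puts symptoms and AEs under an efficacy objective. This stands as to severity: it is a reporting matter in the secondary analyses. It does not remove the filing, since nothing in 8.3.2 exempts vital signs and SAP 11 records no addition.

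Several stronger readings are tempting and should not be drawn:

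- A reader might infer that fatigue, too, could be presented as support for efficacy. The expected drug effect is more fatigue, which would appear as an unfavourable result. It blurs a harm with a pain outcome; it does not favour the drug.
- A reader might infer that no between-arm comparison of vital signs is planned. One is, in the mixed model; what is missing is one in the Safety population.
- A reader might assume that participants are normotensive. Protocol 4.2 excludes uncontrolled hypertension and systolic pressure below 90 mm Hg, not controlled hypertension.
- A reader might call a significant heart-rate result near-certain. At the low end of the assumptions, power is 79%.

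**Conclusion.** The point holds for systolic pressure, diastolic pressure and heart rate. They are safety or pharmacodynamic measures listed as secondary efficacy variables, outside the protocol's named endpoints and without a recorded change. Under the assumptions of 90 per arm and an SD of 10 to 12 bpm, the heart-rate test alone has about 79% to 92% power at 5 bpm and over 99% at 8 bpm, whether or not pain improves. Those effects and SDs are assumed, not taken from the documents.

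The limits are clear. A reader might infer that the trial's main conclusion is at risk, but the primary test of the pain index at Visit 4 does not use these variables. Nor is this mainly a multiplicity problem, as the small change from 87.8% to 85.0% shows. For fatigue, only the label is wrong. The changes should be made, but the primary analysis does not depend on them.

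**What to change.** 1. Remove the vital signs row from SAP Table 8-1.
2. In SAP 9.4, report the between-arm difference with 95% confidence interval for systolic pressure, diastolic pressure and heart rate at each visit, in the Safety population, labelled as safety or pharmacodynamic measures.
3. If counts below heart rate 55 or systolic pressure 90 are shown, present them against baseline. Protocol 4.2 allows entry below 55 after review by the site cardiologist, so some participants may start there.
4. Take weekly fatigue out of the facial pain variables and label it a symptom or tolerability outcome, stating which direction is unfavourable.
5. Record both reclassifications in SAP 11.

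The cost is SAP wording and one added safety table, with no new data. A few P-values would no longer be reported as efficacy. The pain outcomes and the primary analysis stay as they are.
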